6. SUBJECT RECRUITMENT AND ENROLLMENT

Study participants will be recruited from the patient populations of the Breast Oncology Center at the Dana-Farber Cancer Institute.

We will utilize multiple active recruitment techniques to maximize participation and generalizability. We will use the following strategies to identify potential participants:

- Review of clinic schedules and patient lists for medical oncologists at Dana-Farber Cancer Institute to identify patients with Stage I-III breast cancer who are undergoing adjuvant endocrine therapy. HIPAA waivers will be obtained from the DF/HCC IRB to review these patient lists.
- Advertisements in patient areas (see appendix IX. for the brochure of study)
- Advertisement of the study to DFCI patients that are on relevant listservs (e.g., DFCI's Young and Strong newsletter) (see Appendix X).
- Advertisement of study via the "Rally with Partners" newsletter. Rally with Partners is an online platform that shares research opportunities with members of its listserv (see Appendix XI).

For potential participants identified through patient lists, we will contact providers (medical oncologists) and request permission to contact their patients. Providers will be asked to indicate any patients who should not be approached regarding participation in this study. Once potential participants are identified, they will be contacted during a clinic visit or through mailings. For patients with upcoming clinic visits, the research coordinator will approach potential patients in clinic. For patients without an upcoming clinic visit, invitations letters will be mailed with a reply card to indicate interest and an opt-out card (see Appendix VIII for recruitment letters that will be send to potential participants). For patients who are self-identified through advertisements in clinic or respond to advertisements in newsletters/listservs, we will obtain permission from a treating physician before speaking to patients about participation in the study.

Interested subjects identified through these recruitment strategies will be screened by study staff either in person or by phone initially. A screen form based on the Daily Hot Flash Diary will be used to document the frequency and severity of hot flashes, and if potentially eligible, study staff will contact the patient to schedule a visit to review the protocol and sign informed consent. All participants must have the approval of a treating provider in order to participate in the study.

6.1 Registration Procedures

6.2 General Guidelines for DF/HCC Institutions

Institutions will register eligible participants in the Clinical Trials Management System (CTMS), in which OnCore will be used for subject registration. Registration must occur prior to the initiation of any protocol intervention. Any participant not registered to the protocol before protocol intervention begins will be considered ineligible and registration will be denied.

An investigator will confirm eligibility criteria and a member of the study team will complete the protocol-specific eligibility checklist.

Following registration, participants may begin the protocol intervention. Issues that would cause delays should be discussed with the Overall Principal Investigator (PI). If a participant does not receive the protocol intervention following registration, the participant's registration on the study must be canceled. Registration cancellations must be made in OnCore as soon as possible.

6.3 Registration Process for DF/HCC Institutions

DF/HCC Standard Operating Procedure for Human Subject Research Titled *Subject Protocol Registration* (SOP #: REGIST-101) must be followed.

7. SPECIMEN/DATA COLLECTION PROCEDURES

Data Collection:

We plan to use REDCap (Research Electronic Data Capture) for collecting patient-reported outcome data in an encrypted tablet in this study. REDCap is a free, secure, HIPAA compliant web-based application hosted by Partners HealthCare Research Computing, Enterprise Research Infrastructure & Services (ERIS). Vanderbilt University, with collaboration from a consortium of academic and non-profit institutional partners, developed this software application for electronic collection and management of research and clinical study data. Data collection is customized for each study or clinical trial by the research team with guidance from ERIS REDCap administrators. REDCap's stream-lined process for rapidly developing databases requires little database design experience. REDCap provides a user-friendly interface to program web-based case report forms with real-time data entry validation. REDCap is built around HIPAA guidelines and is 21 CFR Part 11 capable. Data collected from REDCap can be easily exported to common data analysis packages: Microsoft Excel, SAS, Stata, R, or SPSS for analysis.⁴⁷ The REDCap study database will be password protected and will be stored on a secure network drive.

In REDCap, data validation checks will be performed at the time of the data submission, and onscreen error and caution messages will inform the study staff of any inconsistencies so that the data can be corrected immediately. Programmatic data validation checks will be conducted by the biostatistician, and the biostatistician will collaborate with the study staff to resolve any data inconsistencies.

Baseline data collection will take place after informed consent, but prior to revealing the intervention assignment. The baseline assessments will be repeated at the end of the 10th week, and end of the 20th week (post crossover). In addition, the Hot Flash Diary will be repeated at two more time points, 5th week and 15th week. Study measures will be collected according to the following schedule (Table 1.):

Participants who complete all the study surveys/logs will receive a \$10 incentive gift card at week 10 and again at week 20.

Table 1. Schedule of Study Measures:

Measures						
Study Phase	Screening	Baseline	Treatment		Crossover/follow-up	
Week	-1	0	5	10	15	20
Consent form		X				
Demographics	X	X				
DHFD (7days)	X	X	X	X	X	X
FACT-B		X		X		X
FACT-ES		X		X		X
PSQI		X		X		X
Actigraphy		X		X		X
Blood Sample Collection		X		X		
Medication/Supplements Log		X		X		X
Sleep Diary		X		X		X
Insomnia Severity Index		X		X		X
AES		X				
NCI-CTCAE			At each acupuncture session (20 or 10) per study arm			
ATF			At each acupuncture session (20 or 10) per study arm			

Note: DHFD: Daily Hot Flash Diary; FACT-B: Functional Assessment of Cancer Therapy- Breast Cancer; FACT-ES: Functional Assessment of Cancer Therapy-Endocrine Subscale; PSQI: Pittsburgh Sleep Quality Index; NCI-CTCAE: the National Cancer Institute-Common Terminology Criteria for Adverse Events; AES: Acupuncture Expectancy Scale; ATF: Acupuncture Treatment Form

Study measures will be collected by the study CRCs. Assessments will be coordinated with acupuncture visits whenever possible, so that patient convenience is maximized. The following measures will be collected:

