8.2 Usual Care

Usual care in the current study is defined as the current standard of care with non-hormonal pharmacotherapy of western medicine.⁴⁶ Participants should not receive acupuncture or acupuncture-like therapy during the usual care portion of study follow-up.

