9.2 Procedures for AE and SAE Recording and Reporting

Participating investigators will assess the occurrence of AEs and SAEs at all participant evaluation time points during the study.

All AEs and SAEs whether reported by the participant, discovered during questioning, directly observed, or detected by physical examination, laboratory test or other means, will be recorded in the participant's medical record and on the appropriate study-specific case report forms.

The descriptions and grading scales found in the revised NCI Common Terminology Criteria for Adverse Events (CTCAE) version 4.0 will be utilized for AE reporting. All appropriate treatment areas should have access to a copy of the CTCAE version 4.0.

A copy of the CTCAE version 4.0 can be downloaded from the CTEP website at:

http://ctep.cancer.gov/protocolDevelopment/electronic_applications/ctc.htm.

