9.4 Reporting

9.4.1 Serious Adverse Event Reporting

All serious adverse events that occur after the initial dose of study treatment, during treatment, or within 30 days of the last session of treatment must be reported to the Principal Investigator/co-PIs on the SAE form. This includes events meeting the criteria outlined in Section 9.1.2, as well as the following:

Grade 2 (moderate) and Grade 3 (severe) Events – Only events that are unexpected and possibly, probably or definitely related/associated with the intervention.

All Grade 4 (life-threatening or disabling) Events – Unless expected AND specifically listed in the protocol as not requiring reporting.

All Grade 5 (fatal) Events – When the participant is enrolled and actively participating in the trial OR when the event occurs within 30 days of the last study intervention.

Participating investigators must report each serious adverse event to the Principal Investigator/Co-PIs within 24 business hours of learning of the occurrence. In the event that the participating investigator does not become aware of the serious adverse event immediately (e.g., participant sought treatment elsewhere), the participating investigator is to report the event within 24 business hours after learning of it and document the time of his or her first awareness of the adverse event. Report serious adverse events by telephone, email or facsimile to:

[name], MB, MPH, PHD

[contact] (phone)

[contact]

And

[name]

[contact] (phone)

[contact]

[contact] (fax)

Within the following 24-48 hours, the participating investigator must provide follow-up information on the serious adverse event. Follow-up information should describe whether the event has resolved or continues, if and how the event was treated, and whether the participant will continue or discontinue study participation.

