9.6 Monitoring of Adverse Events and Period of Observation

All adverse events, both serious and non-serious, and deaths that are encountered from initiation of study intervention, throughout the study, and within 30 days of the last study intervention should be followed to their resolution, or until the participating investigator assesses them as stable, or the participating investigator determines the event to be irreversible, or the participant is lost to follow-up. The presence and resolution of AEs and SAEs (with dates) should be documented on the appropriate case report form and recorded in the participant's medical record to facilitate source data verification.

For some SAEs, the study sponsor or designee may follow-up by telephone, fax, and/or monitoring visit to obtain additional case details deemed necessary to appropriately evaluate the SAE report (e.g., hospital discharge summary, consultant report, or autopsy report).

Participants should be instructed to report any serious post-study event(s) that might reasonably be related to participation in this study. Participating investigators should notify the DF/HCC Principal Investigators and their respective IRB of any unanticipated death or adverse event occurring after a participant has discontinued or terminated study participation that may reasonably be related to the study.

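### Table 1 schedules the CTCAE enquiry only at acupuncture sessions, so it does not carry out the adverse-event assessment that Section 9.2 requires in both arms

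*Combined protocol and SAP*

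**What the plan says.** **Schedule.** The text of Section 7 says that study measures follow Table 1, and that the baseline assessments are repeated at weeks 10 and 20. The hot flash diary is also collected at weeks 5 and 15. The NCI-CTCAE row has no mark at any week; its one entry is "At each acupuncture session (20 or 10) per study arm". Section 8.4 has the same trigger: people receiving acupuncture are asked at each treatment about events related to it. Participants are also given a telephone number for reporting such events.

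**Rule.** Under Section 9.2, investigators "will assess the occurrence of AEs and SAEs at all participant evaluation time points during the study". The sentence makes no distinction by arm. Section 9.1.1 counts an event as adverse whether or not it is related to the study, from the first study treatment or any protocol procedure.

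**SAE window.** The lead sentence of Section 9.4.1 covers SAEs "that occur after the initial dose of study treatment, during treatment, or within 30 days of the last session of treatment", to be reported to the principal investigator within 24 business hours. Section 9.6 follows events "from initiation of study intervention, throughout the study, and within 30 days of the last study intervention".

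**The concern.** Section 9.2 states a rule for both arms, and the schedule that staff work from implements it only where there is a needle session. Controls do have evaluation time points in the randomised period (the diary at week 5, the full set at week 10), but Table 1 attaches no adverse-event enquiry to them. The same is true of the immediate arm at weeks 15 and 20.

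Staff who schedule from Table 1 alone would make no planned enquiry of any control before crossover. Staff who also apply Section 9.2 would. What is collected then depends on which section a coordinator follows. If events were later shown by arm for weeks 1-10, a difference could reflect how often people were asked.

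The SAE wording adds a smaller uncertainty. *Dose* and *session* in Section 9.4.1 suggest acupuncture, which controls first receive in week 11. It is then unclear when the 24-business-hour clock applies to a control SAE before that, for example a Grade 3 hospitalisation.

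**Working it through.** **Inputs.** Immediate arm: 2 sessions a week for 10 weeks, then none. Control arm: none for 10 weeks, then 1 a week for 10 weeks (Sections 5 and 8.1). Randomised: 40 per arm (Section 10.1). Post-baseline time points in Table 1: weeks 5, 10, 15 and 20. Full attendance and follow-up are assumed.

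**1. The plan's own figure.** 2 × 10 = 20 and 1 × 10 = 10. This reproduces the 20 or 10 in the CTCAE row.

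**2. The same enquiries, split by period.**

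| Period | Immediate, per participant | Control, per participant | All participants |
|---|---|---|---|
| Weeks 1-10 | up to 20 | 0 | 40 × 20 = 800 v 0 |
| Weeks 11-20 | 0 | up to 10 | 0 v 40 × 10 = 400 |

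Section 9.2 would need at least the week-10 assessment for controls in the first row and the week-20 assessment for the immediate arm in the second. Table 1 supplies neither.

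**3. After entering weeks 10 and 20 for both arms.** Section 7 coordinates assessments with acupuncture visits where possible, so in the arm then receiving acupuncture the added enquiry may coincide with a session.
- Weeks 1-10: immediate 20 + (0 or 1) = 20 or 21; control 0 + 1 = 1.
- Weeks 11-20: immediate 0 + 1 = 1; control 10 + (0 or 1) = 10 or 11.

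If weeks 5 and 15 are added too, the counts become 20 to 22 v 2, then 2 v 10 to 12. Controls would then have 40 × 2 = 80 scheduled enquiries before crossover, against 0 now.

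**4. The lead-sentence window in Section 9.4.1, under two readings.** 30 days is 30/7 = 4.29 weeks.
- *Study treatment means acupuncture only.* With the last session at week 10 or 20, the window runs over about weeks 0 to 14.3 (immediate) and 10 to 24.3 (control). Control time before it opens is 40 × 10 = 400 of 40 × 20 = 800 person-weeks. In the immediate arm it closes 10 − 4.29 = 5.7 weeks before week 20.
- *Usual care also counts.* The control gap at the start is 0.

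**5. Which reading fits better.** Usual care is defined in Section 8.2 ("Usual care in the current study is defined as the current standard of care"), under a Section 8 heading that names study interventions in the plural. Sections 10.3.1 and 10.4 refer to both groups as intervention arms. Section 6.2 requires cancellation of a registration if the protocol intervention is not received, which fits controls poorly if usual care is not an intervention. Against this, Section 5 gives the label intervention arm to the immediate group alone. On balance, Section 9.6 is better read as covering controls from the start.

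**The case against.** The strongest reply is that the duty already exists. Section 9.2 covers both arms and requires all events to be recorded. Section 9.4.2 sends non-serious events to the principal investigator with no limit by arm. Table 1 lists measures collected by coordinators, whereas Section 9.2 gives adverse-event assessment to investigators, so an incomplete row does not cancel the rule. All of this is correct, and it means that the requirement is not absent. It does not remove the mismatch: Table 1 does carry a CTCAE row, and that row omits time points the rule includes.

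A reader might go further and infer that control SAEs before week 11 go unreported, or that 400 of 800 control person-weeks lie outside SAE reporting. The documents do not support this. Section 9.5 sends all SAEs to the IRB office through the principal investigators, who must therefore learn of them. Section 9.6 is better read as covering controls. Within Section 9.4.1 the Grade 5 line has its own window ("When the participant is enrolled and actively participating in the trial"), and the Grade 4 line ("All Grade 4 (life-threatening or disabling) Events") states no timing. Section 9.3 also defers to DF/HCC requirements that are not reproduced. What remains is an unclear clock for some control SAEs.

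A reader might also see a conflict of scope, because Sections 7.8 and 8.4 name acupuncture-related events while the form in Appendix VI asks about any CTCAE event. The wider question includes the narrower one and the form records attribution, so this is minor.

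Nor can a biased safety comparison be inferred, since no by-arm adverse-event analysis is planned.

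**Conclusion.** The point holds as a conflict between a stated schedule and a stated rule. Table 1 and Section 8.4 do not carry out Section 9.2 for controls in weeks 1-10 or for the immediate arm in weeks 11-20. The size is up to 20 v 0 scheduled enquiries per participant in the randomised period, and 0 v up to 10 afterwards, at full attendance. It concerns scheduled enquiry only: spontaneous reports, and assessments made directly under Section 9.2, are not excluded. The number of events that might be missed cannot be estimated from the documents.

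The SAE window is a secondary wording point. Section 9.4.1 leaves the 24-business-hour clock unclear for some control SAEs before week 11, while the better reading of Sections 9.2, 9.5 and 9.6 already covers those events. The primary and secondary endpoints, the power figures and the planned analyses are untouched. The change is worth making because it affects what safety data are collected and costs very little.

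**What to change.** 1. In Table 1, enter the Section 9.2 CTCAE assessment for both arms at the existing week-10 and week-20 assessments at least. Either add the week-5 and week-15 diary contacts or state that they are not evaluation time points under Section 9.2. Align Section 8.4 with the result.
2. Reconcile Sections 9.1.1, 9.4.1 and 9.6 to one SAE window that applies to both arms. Define *study treatment* and *study intervention*, and say whether the Grade 4 line follows the lead-sentence window.
3. If adverse events are summarised by arm, state that the frequency of enquiry differed. Item 1 gives controls at least one scheduled enquiry before crossover but does not equalise the arms (20 or 21 v 1 in weeks 1-10 if only weeks 10 and 20 are entered).

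The cost is a wording amendment, a few questions at existing contacts and slightly more adverse-event data. The protocol already contains a results summary (Appendix XVI), whose side-effect statement covers only acupuncture-related events. For participants who have finished, only item 3 can still be acted on.

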7.1 Daily Hot Flash Diary (DHFD)

The Daily Hot Flash Diary (DHFD) was originally developed by North Central Cancer Treatment Group (NCCTG).⁴⁸ It is a validated, reliable method for collecting subjective data of both frequency and severity of hot flashes. Participants are also asked to record the frequency of hot flashes and the severity of hot flashes on a scale ranging from 1 to 4 (1, mild; 2, moderate; 3, severe; 4, very severe) each day. The mean hot flash score (HFS) is calculated by multiplying the frequency by the severity of hot flashes recorded in the daily diary. DHFD and its generated HFS have been extensively used in many interventional trials in breast cancer populations, including pharmaceutical and non-pharmaceutical such as acupuncture trials. It has been noted that in using the DHFD, patients on the placebo arm have reported a reduction of hot flashes by mean of 1.5 hot flashes per day (24% reduction) and 2.8 score units (26% reduction) from baseline to the end of first 4 weeks. In the current study, the diary will be administered verbally by study staff prior to enrollment, and recorded daily for 7 days before starting 1st acupuncture as baseline, then daily for 7 days during week 5, week 10, week 15 and week 20. The weekly average hot flash scores (HFS) will be used as the primary endpoint of the study.

7.2 Functional Assessment of Cancer Therapy-Breast (FACT-B)

The FACT-B is a breast cancer-specific Quality of Life instrument of the FACIT system, which consists of FACT-General (FACT-G) and breast cancer subscale (BCS).⁴⁹ It has the following subscales: physical well-being (7 items), functional well-being (7 items), emotional well-being (6 items), social/family well-being (7 items), and breast cancer subscale (10 items). A total FACT-B score is calculated by summing the subscales. The instrument has a total of 37 items asking respondents to rate how true each statement is for the past 7 days. Response scales range from 0 (not at all) to 4 (very much). The breast cancer subscale is a 10-item self-report subscale intended to assess quality of life for breast cancer specific concerns. This subscale assesses common issues for women who have undergone treatment for breast cancer such as hair loss, feelings of attractiveness, and ability to feel like a woman. The FACT-B demonstrates good internal consistency (Cronbach's $\alpha=0.88$) and discriminative validity, and is sensitive to change. A minimal clinically important difference (MCID) has been defined as 7-8 points on total FACT-B score, 2-3 points on the BCS, and 5-6 points on the Trial Outcome Index (TOI).⁵⁰ The Trial Outcome Index is a simple sum of the Physical Well-Being and Functional Well-Being, and BCS, is intended as a summary index of functional status to be used as a clinical trials endpoint.

7.3 Functional Assessment of Cancer Therapy-Endocrine Subscale (FACT-ES)

FACT-ES was developed to be typically used in combination with the FACT-B. The FACT-ES is intended to assess quality of life in breast cancer patients on endocrine therapies.⁵¹ In addition to 5 subscales in FACT-B, the FACT-ES contains an additional 19-item endocrine symptom subscale that specifically assesses menopausal symptoms, including hot flashes, vaginal dryness,

and loss of libido. FACT-ES was validated in women with breast cancer receiving endocrine therapy and has been used in clinical trials.^{52, 53} The FACT-ES demonstrates good internal consistency, test-retest reliability, and sensitivity to change. Same as FACT-B, the higher scores indicated an improvement in quality of life or well-being.

7.4 Pittsburgh Sleep Quality Index (PSQI)

The PSQI is a 19-item self-reported questionnaire that assesses sleep quality for the preceding month. This measure has been validated. The majority of studies report Cronbach α values of 0.70 to 0.83. For the purposes of this study, the questionnaire was modified to ask about sleep quality for the preceding 48 hours. Other studies have also previously altered the PSQI to measure shorter time periods, and researchers have justified this by noting that more recent events might be easier to remember and less impacted by recall bias. PSQI questions are grouped into 7 equally weighted component scores, on a 0 to 3 scale, that are summed to yield a global PSQI score. The global score ranges from 0 to 21, and the higher the score, the worse the sleep quality. A global score of >5 indicates subjective insomnia, which has been used as a cutoff point to investigate clinically significant sleep problems.⁵³⁻⁵⁵

7.5 Actigraphy Movement Device:

The Actigraphy is a wristwatch-like electronic accelerometer-based physical activity device that is used to determine wake versus sleep state based upon movements. It is worn continuously (24 hours/day, 7 days/ week) on either arm for the period of measurement.⁵⁶⁻⁵⁸ The output is in the form of number of movements per unit of time. The pattern of movement has been used as an objective measure for sleep, and correlates for fatigue. The following data will be measured: a. counts per hour of time in bed; b. efficiency, defined as the number of hours slept over the number of hours spent in bed multiplied by 100 (%); c. average awake time (minutes) per hour of sleep; and d. number of awakenings per hour of sleep. Counts are based on the frequency and intensity of the acceleration at each 60-second epoch and are calculated by the software.

Participants will wear the Actigraphy wrist watch for one week at baseline and one week at week 10 and week 20 to record measures of sleep-wake schedules and sleep quality. A number of studies have demonstrated the reliability, validity, utility, accuracy, and responsiveness of this approach in differentiating between physical and sedentary activities and determining the level of daily activity ($p < 0.0001$). Test-retest reliability was very high for 12 different activities ($r=.98$). This device has been shown to be a useful tool in correlative and intervention studies of sleep and fatigue in breast cancer populations.⁵⁶ One study team member will be responsible for cleaning and scoring all sleep data for the selected participants.

